### 9.4. Data Sources

#### 9.4.1. CMS Medicare Administrative Database

The study will use the CMS Medicare administrative database with monthly data refreshes that include Medicare Parts A, B and D. The study will be restricted to enrollees with FFS. The Medicare claims database includes well-defined longitudinal data that captures healthcare service utilization for millions of enrollees across multiple care settings. Medicare Part A captures the inpatient setting, including critical access hospitals and skilled nursing facilities; approximately 90% of inpatient claims are submitted in 2 months after a healthcare

<sup>10 Presence of any concurrent vaccination.

encounter. (18) Medicare Part B covers doctors' services and outpatient care, including outpatient emergency department and outpatient non-emergency department, as well as professional services non-laboratory and laboratory. Medicare Part D covers the pharmacy setting. Medicare claims data undergo three stages of processing: enumeration, adjudication, and final payment. The monthly data consists of a mixture of pre-adjudicated and adjudicated claims; prior research shows that the diagnosis codes rarely change (<0.5%) after adjudication. (12, 14, 15) The use of adjudicated and pre-adjudicated claims data in this study enables near real-time assessment of a potential safety signal.

In this study, the variables will be identified within the relevant care settings. The IP setting represents hospital inpatient acute facility claims, which provide information on the care and services received by patients during the entire duration of inpatient care. These have more accurate diagnosis coding compared to professional claims, as provider facilities are reimbursed based on the types of diagnosis coded, which reflect the level of treatment required. The OP/PB setting represents all outpatient and professional services claims with non-laboratory places of service and captures the broad spectrum of outpatient care regardless of care setting or provider type. Claims with laboratory places of service are excluded as they often include "rule-out-diagnoses" that may not reflect true existing or underlying conditions present in patients.

The demographics of the Medicare FFS population and the coding system used in CMS Medicare data are substantial topics that encompass the broad characteristics of Medicare beneficiaries and the complex system for coding healthcare services, respectively. Below is an overview of both:

The Medicare FFS program covers a diverse population of older adults and some younger beneficiaries with disabilities. The majority of Medicare beneficiaries are aged 65 years of age or older, reflecting Medicare's role as a health insurance program for older adults. The distribution between male and female beneficiaries in the Medicare FFS population tends to reflect that of the older adult population in the U.S., with a higher proportion of females, especially among the oldest age groups.

Medicare beneficiaries come from diverse socioeconomic backgrounds, but the program plays a critical role for lower-income individuals who might otherwise be unable to afford health insurance. The health status of Medicare FFS beneficiaries vary widely, from healthy individuals to those with multiple chronic conditions and serious disabilities. The program covers many individuals with high healthcare needs and expenditures. Medicare FFS beneficiaries are located across the United States, including both urban and rural areas, with distribution patterns reflecting the broader population distribution.

Medicare data utilizes several coding systems to document diagnoses, procedures, and equipment used in the care of beneficiaries. These include ICD-10-CM, used for diagnosis coding in all healthcare settings; ICD-10-PCS (Procedure Coding System), used for inpatient hospital procedure coding; CPT, used in billing process for medical procedures in medical, surgical, and diagnostic services in OP/PB services; HCPCS, also used for medical procedures, such as ambulance services and durable medical equipment; and NDC, used for a

prescription drug billing. The use of these coding systems ensures that Medicare billing is standardized, allowing for the efficient processing of claims and the collection of data for analysis and policy development.

# 9.4.2. IQVIA PharMetrics Plus Commercial Claims Database

The PharMetrics Plus database is one of the largest US health insurance claims databases comprised of fully adjudicated medical and pharmacy claims with approximately 3.1 million annual enrollees aged 60 to 64 years. Data contributors are largely commercial health plans, with an approximate 6-month data lag due to claims adjudication. PharMetrics Plus has diverse representation of geography, employers, payers, providers, and therapy areas, therefore the database is representative of the commercially insured US national population for individuals under 65 years of age. In the post-launch and in-market phase, PharMetrics Plus has been utilized in providing robust insights in areas such as comparative effectiveness, medication adherence, patient cost analyses and also aids in pharmacovigilance and safety by tracking and analyzing the adverse effects of medications and vaccines. (20)

The comprehensive patient insights provided by PharMetrics Plus are driven by several key attributes. For patient demographics, it includes the year of birth, gender, ZIP3 (the first three digits of the ZIP code), state, enrollment dates, and payer/plan type. PharMetrics Plus also details primary care and specialty visits, capturing event dates, diagnosis codes, ordered laboratory tests, procedure codes, and provider specialties, providing understanding of the nature of healthcare interactions of patients. Additionally, the information of medication use can be captured with data on fill and refill dates, retail, mail order, specialty medications, formulary status, status medications, quantity and days supplied, providing a comprehensive view of medication adherence and usage patterns.

Furthermore, the data offers insights into hospital admissions and discharges, including admission dates, inpatient length of stay, discharge status, diagnosis codes, inpatient procedures, ER visits, and provider specialties, enabling the assessment of healthcare utilization and patient outcomes. Similarly, for outpatient medication and vaccine administration, PharMetrics Plus records the date of administration, diagnosis codes, service units, procedure codes and provider specialties, ensuring comprehensive tracking of outpatient care.

### 9.5. Study Size

### Medicare

All eligible Medicare beneficiaries aged 65 years of age or older who receive ABRYSVO during the surveillance period will be included. There were approximately 1,155,000 individuals vaccinated with ABRYSVO through February 2024; from prior experience, with approximately 15% attrition due to the requirement of continuous enrollment in Medicare Parts A, B and D, ~1 million individuals are expected to be eligible for the 2023/2024 season analysis. Assuming a similar uptake for the 2024/2025 season, for the pooled analysis, a sample size of ~2 million ABRYSVO exposures are anticipated by the end of study period.

Table 1 outlines the sample size calculations required for a conditional Poisson regression using the SCRI design, across different Incidence Rate Ratios (IRR). To detect a lower IRR, the total number of GBS events needed increases, as does the number of vaccinated individuals required for both risk intervals. Specifically, to detect an IRR of 5.0, 15 GBS events are needed, with 1,153,846 and 566,038 vaccinated individuals for analysis in the 21day and 42-day post-vaccination risk intervals, respectively. Conversely, to detect an IRR of 2.0, 69 GBS events are needed, with significantly higher requirements of 8,846,154 and 4,339,623 individuals for the 21-day and 42-day post-vaccination risk intervals, respectively. Based on an expected background rate of 4.6 per 100,000 person-years for incident GBS in the Medicare population aged 65 years of age or older (25) and estimated uptake of ABRYSVO in the Medicare FFS dataset from 2023/2024 RSV season, the study is anticipated to be able to detect a high risk of GBS (5.0- fold or lower) with 80% power and an alpha level of 0.05 during a 21- or 42-day risk interval following vaccinations in each RSV season. Pooled analysis combing data from 2 RSV seasons is anticipated to have 80% power to detect a modest risk of GBS (e.g., 3.0- to 4.0-fold), depending on the length of the risk interval. Pfizer has an ongoing PMR PASS (protocol # C3671031) spanning 4.5 RSV seasons (or more) aiming to detect a 2-fold increased risk of GBS following ABRYSVO vaccination using the fully adjudicated CMS Medicare claims. The current PASS described in this protocol (protocol # C3671054) is aimed to generate rapid safety evidence to help rule out a modest or high risk of GBS until the results of the PMR PASS (protocol # C3671031) are available.

Table 1. Sample Size Calculations for the Conditional Poisson Regression Using the SCRI Design

IRR	Total number of GBS events needed	Number of events expected in control interval	Number of vaccinated individuals needed for 21-day period (N)	Number of vaccinated individuals needed for 42-day period (N)
5.0	15	3	1,153,846	566,038
4.5	17	4	1,538,462	754,717
4.0	20	4	1,538,462	754,717
3.5	23	6	2,307,692	1,132,075
3.0	29	8	3,076,923	1,509,434
2.5	41	12	4,615,385	2,264,151
2.0	69	23	8,846,154	4,339,623

Notes: Sample size calculations for the SCRI design were performed according to the method by Musonda et al.(26) The calculations are based on assuming a two-sided  $\alpha$ =0.05, a power of 80%, and a risk interval of 21 and a control interval of 21 days. Calculations were also performed using a 42-day risk interval and a 42-day control interval for secondary analyses. These calculations are based on an equal length of the control and risk interval and provide a conservative estimate of sample size as compared to calculations based on variable lengths of the control and risk interval.

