**Data sources:** The study will use the CMS Medicare databases with monthly data refreshes that include Medicare Parts A, B and D, and PharMetrics Plus commercial claims database. They are both claims databases that include well-defined longitudinal data that captures healthcare service utilization for millions of enrollees across multiple care settings including inpatient, outpatient emergency department and outpatient non-emergency department, professional services non-laboratory and laboratory, and pharmacy settings. The Medicare monthly data consists of a mixture of pre-adjudicated and adjudicated claims; prior research

<sup>2 Goud R, Lufkin B, Duffy J, et al. Risk of Guillain-Barré syndrome following recombinant zoster vaccine in Medicare beneficiaries. JAMA Intern Med. 2021;181(12):1623-30.

<sup>3 Perez-Vilar S, Hu M, Weintraub E, et al. Guillain-Barré syndrome after high-dose influenza vaccine administration in the United States, 2018-2019 season. J Infect Dis. 2021;223(3):416-25.

shows the diagnosis codes rarely change (<0.5%) after adjudication. The PharMetrics Plus data consists of fully adjudicated claims.

**Study size:** All Medicare and commercially insured older adults who meet the eligibility criteria during the study period will be included. The sample size calculation outlines the number of individuals required for a conditional Poisson regression using the SCRI design, across different Incidence Rate Ratios (IRR). Based on preliminary counts through February 2024, approximately 1 million ABRYSVO-vaccinated individuals aged 65 years of age or older are expected to be included in the study for one RSV season. The study is anticipated to have 80% power to be able to detect a high to modest increased risk of GBS (5.0- fold or lower) in each RSV season. Pooled analysis combing data from 2 RSV seasons is anticipated to have 80% power to detect a modest increased risk of GBS (3.0- to 4.0- fold). Given the limited age range for commercially insured adults 60-64 years, analyses for this age group will be primarily descriptive.

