### 9.7.4. The Statistical Analysis for the SCRI

In the SCRI methodology, each ABRYSVO-vaccinated beneficiary serves as their own control as we assess the risk of experiencing GBS during a pre-defined post-vaccination risk interval to a post-vaccination control interval within the same individual (Section 9.1.2.1). The study population will include all exposed individuals that meeting the inclusion and exclusion criteria, but only individuals who develop GBS cases will contribute to the analysis. This approach inherently controls for time-invariant confounding variables and is a widely recognized method in vaccine safety research but may be susceptible to time-varying

60+y & 0,1 CCI

<sup>11 Pfizer's preliminary analysis in Optum's de-identified Market Clarity Data, previously presented to the FDA in a document titled "Request for Comments and Advice Regarding RSV Vaccine Safety Study (28 August 2024)".

confounding, which can be minimized by choosing a control interval close to the risk interval.

In the analysis, GBS cases that occurred within the first 84 days following vaccination will be included and separated out into the risk and control window. The population summary statistics will be provided for each window.

A conditional Poisson regression model will be used to estimate the IRR and 95% CI, offset by the length of observation time. The model will include an indicator for the risk window as the predictor variable, an offset equal to the log of the window length and will condition on an identification variable for the beneficiary. The model can be written as:

$$log(p) = \beta(risk \ window) + log(interval) + strata(beneficiary \ id)$$

where *p* is the risk of GBS, *interval* represents the length of the respective window in days, and *beneficiary id* is the term identifying the patient. In the primary analysis, the risk window is 1-21 days post-vaccination, and the control window is 43-84 days post-vaccination. In the secondary analysis, the risk window is 1-42 days post-vaccination, and the control window is 43-84 days post-vaccination. Under this model, our null and alternative hypotheses are:

$$H_0$$
:  $e^{\beta} = 1$  (i.e., IRR = 1)

$$H_a$$
:  $e^{\beta} \neq 1$  (i.e.,  $IRR \neq 1$ )

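### Table 1 overstates the vaccinees needed for the primary 21-day SCRI interval, so it appears to contradict a per-season power statement that is in fact supported

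*Protocol*

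**What the plan says.** Section 9.5 (Medicare) starts from about 1,155,000 recipients through February 2024, removes about 15% for enrolment requirements, and concludes that about "1 million individuals are expected to be eligible for the 2023/2024 season analysis", with roughly 2 million over two seasons. It states that "the study is anticipated to be able to detect a high risk of GBS (5.0- fold or lower) with 80% power", and applies this as "80% power and an alpha level of 0.05 during a 21- or 42-day risk interval following vaccinations in each RSV season". The abstract repeats the claim: "80% power to be able to detect a high to modest increased risk of GBS (5.0- fold or lower) in each RSV season". For the pooled analysis, both places give 3- to 4-fold.

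The same section and Table 1 state that at IRR 5.0 "15 GBS events are needed, with 1,153,846 and 566,038 vaccinated individuals" are required for the 21- and 42-day intervals respectively. The table note gives a two-sided 0.05 level, 80% power, a cited self-controlled case series sample-size method, and, for the 21-day column, "a risk interval of 21 and a control interval of 21 days". The 42-day column uses 42 and 42 days. The note describes equal interval lengths as conservative.

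Section 9.7.4 fixes the analysis itself: "In the primary analysis, the risk window is 1-21 days post-vaccination, and the control window is 43-84 days post-vaccination". The secondary analysis compares days 1-42 with days 43-84.

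**The concern.** Read side by side, the text says the primary interval reaches 80% power at IRR 5.0 in each season, and the table says it does not: 1,153,846 needed against 981,750 to 1 million expected, a gap of 13% to 15%. Only the count before attrition (1,155,000) meets the table. The 42-day column raises no such conflict, because 566,038 is well below 1 million.

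The table also has a visible fault. IRR 4.5 (17 events) and IRR 4.0 (20 events) carry the same sample size in both columns, although the required sample size should rise as the IRR falls, as Section 9.5 itself says.

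These are the only planning figures for the comparative analysis. The study's stated purpose is to help rule out a modest or high risk until the longer study reports, so the reading of a null seasonal result depends on what the design could detect. At present the text and the table give opposite answers for the primary interval.

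**Working it through.** **Inputs.** Background rate 4.6 per 100,000 person-years, two-sided 0.05, 80% power, 1,155,000 recipients and 15% attrition (Section 9.5 and the Table 1 note); windows from the Table 1 note and Section 9.7.4. With a 365.25-day year (my convention; a 365-day year moves the results by less than 0.1%), the risk per 21 days is q = 4.6e-5 × 21/365.25 = 2.645e-6, and per 42 days 5.290e-6. Expected eligible per season: 1,155,000 × 0.85 = 981,750.

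**Formula** (signed-root likelihood-ratio form for self-controlled designs). With r the risk window's share of observed time and d = IRR·r + 1 − r:

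- A = 2[IRR·r·ln(IRR)/d − ln(d)]
- B = (ln IRR)²/A × IRR·r(1 − r)/d²
- events n = (1.960 + 0.842√B)²/A
- power for n events = Φ[(√(nA) − 1.960)/√B]
- vaccinees N = n / [q(IRR + c)], where c = control length / risk length and q is the risk over one risk-window length

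**Step 1: reproduce Table 1.** With r = 1/2 the formula gives 14.86, 16.61, 19.07, 22.74, 28.75, 40.14 and 68.09. Rounded up, these are the table's 15, 17, 20, 23, 29, 41 and 69 events. Every printed N then equals events/(1 + IRR), rounded up to a whole number, divided by 2.6e-6 (21-day) or 5.3e-6 (42-day). At IRR 5.0: 15/6 = 2.5, rounded to 3; 3/2.6e-6 = 1,153,846 and 3/5.3e-6 = 566,038. At IRR 4.5: 17/5.5 = 3.09, rounded to 4. At IRR 4.0: 20/5 = 4. The last two rows therefore share 1,538,462 and 754,717.

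**Step 2: remove the intermediate rounding, keep 21/21 windows.** IRR 5.0: 2.5/2.645e-6 = 945,264, below 981,750. The printed figure is 22% too large: 20% from 2.5 to 3 and 1.7% from 2.645 to 2.6. IRR 4.5 becomes 1,168,690 and IRR 4.0 becomes 1,512,422, so the tie disappears. The 42-day column is affected too: 472,632 instead of 566,038 at IRR 5.0, and 966,270 instead of 1,132,075 at IRR 3.5. Rows whose control count is already whole (IRR 4.0 and 2.0) barely move.

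**Step 3: use the planned primary windows (21/42, r = 1/3, c = 2).** At IRR 5.0, A = 0.6046 and B = 0.8743, so n = 12.48, or 13 events, and N = 13/(7 × 2.645e-6) = about 702,000.

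| IRR | Table 1, 21-day column | 21/21, no intermediate rounding | 21/42 events | 21/42 N |
|---|---|---|---|---|
| 5.0 | 1,153,846 | 945,000 | 13 | 702,000 |
| 4.5 | 1,538,462 | 1.17M | 15 | 873,000 |
| 4.0 | 1,538,462 | 1.51M | 17 | 1.07M |
| 3.5 | 2,307,692 | 1.93M | 21 | 1.44M |
| 3.0 | 3,076,923 | 2.74M | 27 | 2.04M |
| 2.5 | 4,615,385 | 4.43M | 38 | 3.19M |
| 2.0 | 8,846,154 | 8.70M | 68 | 6.43M |

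**Step 4: power at the expected N.** For 981,750 vaccinees at IRR 5.0:

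- 21/21 windows: expected events 981,750 × 2.645e-6 × 6 = 15.58, power 0.82.
- 21/42 windows: expected events 981,750 × 2.645e-6 × 7 = 18.18; √(18.18 × 0.6046) = 3.315; (3.315 − 1.960)/0.935 = 1.45; power 0.93.

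At 1 million vaccinees the values are 0.83 and 0.93.

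**Step 5: IRR detectable with 80% power** at 981,750 per season and 1,963,500 pooled:

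- 21/42 windows: 4.1 per season, 3.0 pooled.
- 42/42 windows: 3.5 per season, 2.6 pooled.

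**The case against.** The strongest reply is that this is a presentational matter that errs on the safe side. The 21/21 choice is stated in the table note and correctly called conservative. The 42-day column uses exactly the secondary analysis windows, so the table as a whole is not built on unused windows. All eligible recipients are included, so Table 1 sets no enrolment target, and Interim report 1 on the first season is already complete. The headcounts are approximate. All of this stands, and it limits the point to a minor one.

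It does not remove the point. The conservative label covers window length only; the rounding of expected events is not disclosed, and it alone creates the conflict at IRR 5.0.

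Three stronger readings are tempting, and the document supports none of them:

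- A reader might infer that the primary analysis is underpowered at IRR 5.0. Removing either defect reverses that: with the roundings gone, N falls to 945,000; with 21/42 windows and the table's rounding kept, it is about 755,000. Both are below 981,750.
- A reader might infer that the pooled 3- to 4-fold statement is wrong. It follows from the printed table at about 2 million (1,538,462 at IRR 4.0 for 21 days; 1,509,434 at IRR 3.0 for 42 days). Recomputed 21/42 power at 1.96 to 2.0 million is about 0.80 at IRR 3.0 and 0.97 at IRR 4.0.
- An exact test with 21/21 windows gives power of only 0.71 to 0.72 at IRR 5.0, but this combines a test other than the cited method with windows the primary analysis does not use. With 21/42 windows the exact test gives 0.86 to 0.87.

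**Conclusion.** The point holds as an error in Table 1 and a mismatch between the table and the text. For the primary interval at IRR 5.0 the printed N is 22% too large for its own stated windows, and about 64% above the roughly 702,000 needed for the planned ones (1,153,846/702,000 = 1.64). The statement of 80% power at IRR 5.0 per season is supported, with power of about 0.93 under the planned design, and it understates what the study can detect.

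This rests on the protocol's 4.6 per 100,000 person-years, its 15% attrition, complete follow-up and the cited sample-size method. A different background rate or accrual would shift all the figures. Neither the secondary windows nor the pooled statement is contradicted.

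**What to change.** Recompute the 21-day column of Table 1 for a 21-day risk and 42-day control window, and recompute both columns without rounding the control-interval expectation or the per-interval risk before deriving N. Amend the note to match. Then restate Section 9.5 and the abstract's study-size paragraph at the post-attrition N: power of about 0.93 at IRR 5.0 per season for the primary interval, and detectable IRRs of about 4.1 per season and 3.0 pooled (21-day) and about 3.5 and 2.6 (42-day).

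The cost is one rerun of a formula and edits in three places. Eligibility, windows, models and timelines do not change.

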### **PharMetrics Plus**

For the PharMetrics Plus analysis, the primary study population will consist of adults 60-64 years of age enrolled in healthcare plans captured in the PharMetrics Plus database without a prior history of GBS as assessed during a 12-month baseline period.

Based on medical and pharmacy claims through December 31, 2023, approximately 46,000 individuals between 60 and 64 years of age received ABRYSVO in the PharMetrics Plus database; 36,000 had one year of continuous medical and pharmacy benefits enrollment prior to ABRYSVO receipt. The PharMetrics Plus analysis will be descriptive in nature; the inferential analysis, SCRI, may be considered contingent on sample size.

# 9.6. Data Management

Datasets will be stored according to the third-party data vendor's procedures, and analytic programs will be stored according to IQVIA procedures with access restricted to study personnel. IQVIA confidentiality agreements are signed by all employees and include data protection and strict prohibitions on reidentification attempts. SAS® software (SAS Institute Inc., Cary, North Carolina, United States) or other appropriate analytical software will be used to access the raw data, manage the analytic datasets, and conduct data analyses. According to CMS Medicare reporting rules, values below 11 will be suppressed for any counts presented in the report.

